7.4.3 Intervention After the End of the Study

There is no intervention planned for patients after the end of the study.

7.5 Precautions and/or Lifestyle Considerations

Prior to the application of the study medication, the identified AD treatment area(s) should be washed and cleaned using the patient's routine cleansing products. The area should be dried completely prior to the application of the study medication. Patients must not wash the treatment area, go swimming, or perform physical exercise that may cause profuse sweating for a period of 6 hours after applying the study medication. While on study, patients should continue to use their routine cleansing and cosmetic products.

Patients may not use a non-therapeutic, bland emollient, moisturizers, or sunscreens on areas being treated with study medication for the duration of the study. Moisturizers, emollients, and sunscreens may be used on areas not being treated with study medication. Patients must take special precautions to try and limit sun exposure to all identified treatment areas by wearing protective clothing and applying sunscreen to areas not being treated with study medication.

7.6 Prior and Concomitant Medications

All medications (including vaccines, over-the-counter or prescription medicines, vitamins, and/or herbal supplements) taken from 3 months before the Screening Visit until the end of the follow-up period will be recorded in the appropriate section of the eCRF. The following details must be recorded in the eCRF:

- Medication name, ideally the generic name
- Reason for use
- Start and end date of administration
- The dose and frequency of administration

The medical monitor should be contacted if there are any questions regarding prior or concomitant medication or procedures.

7.6.1 Prior Medications

Prior medications are defined as medications taken prior to the first dose of study medication and discontinued before the first dose of study medication. Prior medication information will be collected at the Screening Visit and updated, if necessary, on Day 1 prior to the first administration of study medication.

See [Section 15](#) for details of medication that is permitted or prohibited according to the inclusion and exclusion criteria.

7.6.2 Concomitant Medication

Concomitant medications are defined as any medication taken after the first dose of study medication until the Day 42/PTFU Visit.

Concomitant medications (e.g., prescription, over-the-counter, or herbal) should be administered during the study only if they are prescribed for treatment of specific clinical events.

Use of any of the following treatments is prohibited during the study:

- Phototherapy (ultraviolet A, ultraviolet B, or psoralen and ultraviolet A therapy).
- Systemic biologic immunosuppressant or immunomodulatory therapy (e.g., etanercept, alefacept, infliximab, dupilumab).
- Non-biologic immunosuppressants (e.g., methotrexate, retinoids, calcineurin inhibitors, cyclosporine, hydroxycarbamide [hydroxyurea], azathioprine).
- JAK inhibitors (systemic and topical).
- Systemic or topical corticosteroids (intranasal, inhaled, and topical ocular corticosteroids are allowed if used to treat other medical conditions).
- Cytostatic agents.
- Crisaborole.
- Systemic antibiotics.
- Topical treatments for AD (corticosteroids, calcineurin inhibitors, topical H1 and H2 antihistamines, topical antimicrobials, and other medicated topical agents).
- Live attenuated vaccine treatment.
- Other investigational products.
- Use of potent inhibitors of cytochrome P450 3A4 such as (but not limited to) clarithromycin, erythromycin, diltiazem, itraconazole, ketoconazole, ritonavir, verapamil, goldenseal, and grapefruit.

7.7 Overdose

It is not anticipated that ATI-1777 will be systemically absorbed, and dosing will vary between patients. Treatment of suspected overdose with ATI-1777 should consist of clinically appropriate supportive measures.

7.8 Compliance

Site staff will train patients in the correct application of the study medication to each patient and will check that each patient is following the instructions properly. Any deviation from the correct use of the study medication will be recorded in the eCRF. Study staff will counsel the patients, as required to make sure patients are compliant with study medication applications.

The volume of each study medication applied in each application will be recorded in a patient diary, which will be reviewed at each study visit. The investigator or designee will be responsible for monitoring patient compliance through diary review, questioning the patient, documenting missed doses, if any, weighing the bottle before dispensing and after return, and performing a visual inspection of the quantity in the study medication bottles (used and unused). A record of the study medication dispensed to and returned by each patient will be maintained and reconciled with study medication and compliance

records at the site. The study medication start and stop dates, including dates for study medication delays and/or dose reductions, will also be recorded in the eCRF.

7.9 Accountability

The study medication must not be used for any purpose other than that defined in this protocol. All supplies of study medication will be accounted for in accordance with GCP.

The pharmacist or (designee) should maintain accurate records of all study medication supplies received during the study. These records should include the dates and amounts of study medication that were received at the site, dispensed, and destroyed or returned to the sponsor (or designee). The records should include dates, quantities, batch/serial numbers, expiration dates (if applicable), and the unique code numbers assigned to the study medication and study patients. If errors or damage in the study medication shipments occur, the investigator should contact the sponsor (or its designee) immediately. Copies of the study medication accountability records will be provided by each investigator for inclusion in the trial master file. The study monitor will periodically check the supplies of study medication held by the investigator or pharmacist to verify accountability of the study medication used.

Investigators will maintain records that document adequately that the patients were provided the medication specified by the protocol and reconcile all study medication received from the sponsor (or designee).

After the end of the study, all unused study medication and all medication containers should be destroyed at the study center or returned to the sponsor (or designee) for destruction. In either instance, complete documentation will be returned to the sponsor. The study medication resupply will be managed by the IXRS.

8 ADVERSE EVENTS

8.1 Definitions

8.1.1 *Adverse Events*

An AE is any untoward medical occurrence in a patient administered a pharmaceutical product and which does not necessarily have a causal relationship with this treatment. An AE can therefore be any unfavorable and unintended sign (including an abnormal laboratory finding), symptom, or disease temporally associated with the use of a medicinal (investigational) product, whether or not related to the medicinal (investigational) product.

TEAEs are defined as AEs with an onset date on or after the first administration of study medication and before the date of last administration of study medication + 14 days.

8.1.2 *Serious Adverse Events*

An SAE is any event that meets any of the following criteria:

- Results in death.
- Is life-threatening.
- Requires inpatient hospitalization or prolongation of existing hospitalization.
- Results in persistent or significant disability/incapacity.
- Is a congenital anomaly/birth defect.
- Is an important medical event that may not result in death, be life-threatening, or require hospitalization. The event will be considered an SAE when, based upon appropriate medical and scientific judgment, the event may jeopardize the patient and may require medical or surgical intervention to prevent one of the outcomes listed above. Examples of such events include intensive treatment in an emergency room or at home for allergic bronchospasm, blood dyscrasias, or convulsions that do not result in inpatient hospitalization, or the development of drug dependency or drug abuse.

Definition of Terms

Life-threatening: an AE is life-threatening if the patient was at immediate risk of death from the event as it occurred, i.e., it does not include a reaction that, if it had occurred in a more severe form, might have caused death. For example, drug-induced hepatitis that resolved without evidence of hepatic failure would not be considered life-threatening even though drug-induced hepatitis can be fatal. It does not include an AE or suspected adverse reaction that, had it occurred in a more severe form, might have caused death.

Hospitalization: AEs requiring hospitalization should be considered SAEs.

Hospitalization for elective surgery, or for procedures planned prior to the patient providing informed consent, or routine clinical procedures that are not the result of an

AE (e.g., elective surgery for a pre-existing condition that has not worsened) need not be considered AEs or SAEs. If anything untoward is reported during the procedure, that occurrence must be reported as an AE, either 'serious' or 'nonserious' according to the usual criteria.

In general, hospitalization signifies that the patient has been detained (usually involving at least an overnight stay) at the hospital or emergency ward for observation and/or treatment that would not have been appropriate in the physician's office or outpatient setting. When in doubt as to whether hospitalization occurred or was necessary, the AE should be considered serious.

Disability/incapacity: an AE is incapacitating or disabling if the experience results in a substantial and/or permanent disruption of the patient's ability to carry out normal life functions.

8.1.3 Suspected Unexpected Serious Adverse Reactions

A suspected unexpected serious adverse reaction is defined as any AE for which there is a reasonable possibility that the study medication caused the AE (where 'reasonable possibility' means there is evidence to suggest a causal relationship between the study medication and the AE), the AE is not listed in the IB or is not listed at the specificity or severity that has been observed, and the AE meets at least one of the criteria for seriousness (see [Section 8.1.2](#)).

8.1.4 Clinical Laboratory Abnormalities and Other Abnormal Assessments

Laboratory abnormalities without clinical significance should not be recorded as AEs or SAEs. However, laboratory abnormalities (e.g., clinical chemistry, hematology, and urinalysis abnormalities) that require medical or surgical intervention or lead to study medication interruption, modification, or discontinuation must be recorded as an AE or SAE, as applicable. In addition, laboratory or other abnormal assessments (e.g., in ECGs, X-rays, or vital signs) that are associated with signs and/or symptoms must be recorded as an AE or SAE if they meet the definition of an AE or SAE as described in [Sections 8.1.1 and 8.1.2](#). Whenever possible, the underlying cause for clinically relevant laboratory value (e.g., anemia) should be recorded as an AE, rather than the laboratory value itself (e.g., decreased hemoglobin).

For specific information on handling of clinical laboratory abnormalities, see [Section 6.3.2](#).

8.1.5 Adverse Events of Special Interest

The AESIs for this study are TEAEs of:

- Application site AEs
- Serious infections

- Malignancies
- Thrombosis
- Cytopenias
- Liver enzyme elevation AEs (e.g., ALT, AST, bilirubin, GGT, LDH)
- Increased lipid parameter AEs (e.g., TC, LDL-C, HDL-C, TG)

An AESI should be reported by the investigative site using the relevant page of the eCRF. The documentation and processing of AESIs is further detailed in the investigator site file.

8.2 Assessment of Adverse Events

8.2.1 Severity

Severity grading for every AE is to be performed by the investigator based on his/her best medical judgment as follows:

- Mild: asymptomatic or mild symptoms; clinical or diagnostic observations only; intervention not indicated
- Moderate: minimal, local, or noninvasive intervention indicated; limited age-appropriate instrumental activities of daily living
- Severe: medically significant; disabling; or limiting self-care activities of daily living

The terms serious and severe are not synonymous. The general term “severe” is often used to describe the intensity (severity) of a specific event; the event itself, however, may be of relatively minor medical significance (such as a “severe” headache). This is NOT the same as serious, which is usually associated with events that pose a threat to a patient’s life or ability to function (see [Section 8.1.2](#)). A severe AE (classified as “severe” or “life-threatening”) does not necessarily need to be considered serious. For example, a WBC count of 1000/mm³ to less than 2000/mm³ is considered severe but may not be considered serious. Seriousness (not intensity) serves as a guide for defining regulatory reporting obligations.

8.2.2 Causality

Investigators are required to systematically assess the causal relationship between the AEs and SAEs and the exposure to the study medication using the following definitions:

Related:

- The AE follows a reasonable temporal sequence to study medication administration, and it cannot be reasonably explained by the patient’s clinical state or other factors (e.g., disease under study, concurrent diseases, or concomitant medications).

- The AE follows a reasonable temporal sequence to study medication administration, and it is a known reaction to the drug under study or a related chemical group or is predicted by known pharmacology.

Not Related:

- The AE does not follow a reasonable sequence from study medication administration, or it can be reasonably explained by the patient's clinical state or other factors (e.g., disease under study, concurrent diseases, and concomitant medications).

A “reasonable possibility” of a relationship conveys that there are facts, evidence, and/or arguments to suggest a causal relationship, rather than a relationship cannot be ruled out.

8.3 Documenting and Reporting Adverse Events

Reporting of SAEs will begin when the patient has provided informed consent. Nonserious events that occur between receipt of informed consent and the first study medication application will be added to the patient's medical history. Reporting of nonserious AEs will begin with the first application of study medication. Nonserious events that occur between receipt of informed consent and the first study medication application will be added to the patient's medical history. Reporting of all AEs will continue through the PTFU Visit or 14 days after last administration of study medication, whichever is later.

Occurrence of AEs may be volunteered spontaneously by the patient; discovered as a result of general, nonleading verbal questioning by the study staff; or determined by physical examination or other safety assessments. All AEs will be monitored and recorded in the eCRF throughout the entire study.

For all AEs, the investigator must pursue and obtain adequate information (a description of the event, severity, time of occurrence [including whether the AE onset was before, during, or after the study medication application], duration, and any action, e.g., treatment/follow-up tests). The outcome of the event should be provided along with the investigator's assessment of the relationship to the study medication. The investigator must also assess whether the event meets the criteria for classification as an SAE.

It is the investigator's responsibility to review all documentation (e.g., hospital notes, laboratory reports, and diagnostic reports) related to an AE. Wherever possible, the investigator's diagnosis, not the individual signs and symptoms, will be documented as the AE.

Investigators are not obligated to actively seek AEs or SAEs after the patient's conclusion of study participation. However, if the investigator learns of any SAE, including death, at any time after a patient has been discharged from the study, and

he/she considers the event to be reasonably related to the study medication or study participation, the investigator must promptly notify the sponsor.

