8.4 Reporting of Serious Adverse Events

For SAEs with an onset inside the reporting period (i.e., onset after provision of informed consent and up to the PTFU Visit or 14 days after the last application of study medication administration (for SAEs), whichever is later) and SAEs considered related to study medication that occur after this reporting period (e.g., during poststudy follow-up), the investigator must immediately (no later than 24 hours after becoming aware of the event) inform the ProPharma Group of the SAE utilizing the safety report form (see [SERIOUS ADVERSE EVENT CONTACT INFORMATION](#)).

The investigator is obliged to respond to any request for follow-up information (e.g., additional information, event outcome, final evaluation, or other records where needed) or to any question the sponsor (or designee) may have concerning the SAE within the same timelines as those noted above for initial reports. This is necessary to ensure prompt assessment of the event by the sponsor (or designee) and, as applicable, to allow the sponsor to meet strict regulatory timelines associated with expedited reporting obligations for events of this nature.

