9.4 Statistical Methods

9.4.1 *Primary Endpoint*

The primary endpoint is the percent change from baseline in EASI score at Week 4.

9.4.2 *Secondary Endpoints*

The secondary endpoints are:

- Percent change from baseline in EASI score at each study visit
- Proportion of patients achieving an IGA score of 0 to 1 combined with an improvement of 2 or more points from baseline within 4 weeks of the start of treatment
- Proportions of patients who achieve EASI-50, EASI-75, and EASI-90 within 4 weeks of the start of treatment
- Change from baseline in IGA score at each study visit
- Change from baseline in BSA at each study visit
- Change from baseline in PP-NRS score over time

9.4.3 *Pharmacokinetic Endpoint*

The PK endpoint is the concentration of ATI-1777 in plasma samples obtained using a sparse sampling approach.

9.4.4 *Safety Endpoints*

The safety endpoints are:

- Incidence of TEAEs and SAEs
- Laboratory values
- Vital signs
- Physical examination results
- 12-lead ECG results

9.4.5 *Analysis of Efficacy*

All efficacy summaries will be conducted on both the FAS and PP populations. All p-values for efficacy will be based on a 1-sided hypothesis test of the superiority of ATI-1777 to vehicle.

The primary efficacy analysis will be the treatment comparison between ATI-1777 and vehicle for the percent change from baseline in EASI scores at Week 4 based on the FAS. This treatment comparison will be made within the context of a Mixed Model Repeated Measures analysis where the EASI scores over time are treated as repeated measures within a given patient. Treatment group, time (study visit), and treatment by time interaction will enter the model as categorical factors, baseline EASI score and/or baseline severity of AD will be included as a continuous covariate and patient ID will enter the model as a random effect. Treatment group model-based means and model-based differences in treatment groups will be provided along with corresponding 90% confidence intervals and 1-sided p-values.

Treatment comparisons between ATI-1777 and vehicle for each of the continuous efficacy endpoints that are conducted over time (change in IGA, BSA, and PP-NRS) will be analyzed using a similar model as described for the primary endpoint. Treatment comparisons will be made for each post-baseline scheduled visit utilizing an appropriate analysis window scheme.

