10. Nonserious AEs will be collected after the patient's first application of study drug and continue until the patient's last visit. SAEs will be collected from the time the patient signs the ICF until the patient's last visit.

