#### 12.6.1. Adverse Events

An AE is defined as any untoward medical occurrence associated with the use of a drug in humans, whether or not considered drug related.

TEAEs are defined as AEs with an onset date on or after the first administration of study medication and before the date of last administration of study medication + 14 days.

An SAE is defined as any AE that results in any of the following outcomes: death, a life-threatening AE, inpatient hospitalization or prolongation of existing hospitalization, a persistent or significant incapacity or substantial disruption of the ability to conduct normal activities of daily living, or a congenital anomaly/birth defect. Important medical events that may not result in death, be life-threatening, or require hospitalization may be considered SAEs when, based upon appropriate medical judgment, they may jeopardize the patient and may require medical or surgical intervention to prevent one of the outcomes listed in this definition.

The severity of AEs will be classified by the investigator as mild, moderate, or severe.

The causality of AEs will be classified by the investigator as related and not related.

An overall AE summary will be generated presenting the frequency and percentage of patients and the number of AEs using FAS for the following:

- Any TEAE
- Any treatment-related TEAE
- Any severe TEAE
- Any treatment-related severe TEAE
- Any SAE
- Any treatment-related SAE
- Any TEAE leading to study discontinuation
- Any death
- Any Suspected Unexpected Serious Adverse Reaction
- Any Adverse Events of Special Interest

All AEs will be coded using MedDRA (version to be delineated in the clinical study report [CSR]). The TEAEs will also be summarized by SOC, PT, by severity and relationship to study treatment. Missing or partial medication start/stop date will be imputed as described in [Appendix 3](#).

The TEAE summary tables will be sorted by SOC and PT. System organ class will be displayed in descending order of overall frequency then alphabetically. Preferred term will be displayed in descending order of overall frequency and then alphabetically within SOC. A patient with 2 or more events within the same level of summarization will be counted only once in that level using the most severe incident or most related incident. Percentages will be based on the number of patients in the FAS.

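### The *Any SAE* row in SAP 12.6.1 has no first-dose onset condition, so a screening-period SAE in a patient later dosed would count in that patient's arm

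*Protocol*

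**What the plan says.** **Collection.** Protocol 8.3 sets different starting points for serious and nonserious events: "Reporting of SAEs will begin when the patient has provided informed consent", whereas "Reporting of nonserious AEs will begin with the first application of study medication". Nonserious events between consent and first application go to medical history. Protocol 8.4 gives the SAE reporting period as "onset after provision of informed consent and up to the PTFU Visit or 14 days after the last application of study medication administration", whichever is later. Footnote 10 of SAP Table 1 agrees on the start: "SAEs will be collected from the time the patient signs the ICF until the patient's last visit". Screening lasts up to 30 days (protocol 4.1, SAP 8).

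**Definitions.** In SAP 12.6.1, "TEAEs are defined as AEs with an onset date on or after the first administration of study medication" and before 14 days after the last dose. The same section defines an SAE as any AE with one of the listed serious outcomes, with no condition on onset date.

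**Tabulation.** The overall AE summary in SAP 12.6.1 is produced on the FAS. Five of its rows are worded as TEAE rows. *Any SAE* and "Any treatment-related SAE" are not. The endpoint in protocol 9.4.4 also names the two kinds of event separately: "Incidence of TEAEs and SAEs". Protocol 3.4 and SAP 9.1 do the same.

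**Analysis set.** The FAS is all randomised patients with at least one dose, and safety is analysed as treated (SAP 9.2.1). Protocol 9.1 says that all data are presented by treatment group.

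**The concern.** Because earlier nonserious events go to medical history, the pre-dose events expected in the adverse event data are SAEs. The table row that reports SAE incidence is also the one row that does not filter on onset. An event before any exposure cannot be an effect of ATI-1777 or vehicle, yet it would be shown as part of an arm's SAE incidence, a named safety endpoint of a first-in-human study.

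The table could also fail to reconcile: a patient could be counted under *Any SAE* and not under *Any TEAE*. No other summary specified in 12.6.1 would correct the figure. The SOC/PT tables cover TEAEs, SUSARs and AESIs, and SAEs otherwise appear only in a listing.

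**Working it through.** The documents give no SAE rate or count, so there is no stated figure to reproduce. The check compares each row of the SAP 12.6.1 summary with the SAE collection window, then sizes one event.

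**Step 1: which rows can admit a pre-dose event?**

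| Row(s) | What keeps pre-dose events out |
|---|---|
| Five TEAE rows (any, related, severe, related severe, leading to study discontinuation) | The TEAE definition |
| AESI | Defined as TEAEs (SAP 12.6.1.2) |
| Treatment-related SAE | Both limbs of *Related* in protocol 8.2.2 require a temporal sequence to administration |
| SUSAR | Requires evidence that study medication caused the event (SAP 12.6.1.1) |
| Death | The FAS requires a dose, so a patient who dies before dosing is not in the table |
| *Any SAE* | Nothing in the row, in the SAE definition or elsewhere |

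Only one row is open.

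**Step 2: does the SAP expect pre-dose onsets?** Yes. SAP Appendix 3 sets an AE start date with missing day and month to the screening date when its year precedes the first-dose year but matches the screening year.

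**Step 3: weight of one event.**
- Protocol: about 50 patients randomised 1:1, so 25 per arm; 1/25 = 4.0 percentage points.
- SAP: about 42 patients randomised 1:1, so 21 per arm; 1/21 = 4.8 percentage points.

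**Step 4: share of the SAE window before first dose, for a completer.** Share = screening days / (screening days + 28 treatment days + 14 follow-up days).
- 30 days: 30/72 = 41.7%
- 14 days: 14/56 = 25.0%
- 7 days: 7/49 = 14.3%

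Protocol 4.1 gives a maximum duration of 73 days rather than 72; 30/73 = 41.1%, so the difference is immaterial. These are shares of calendar time, not predicted shares of SAEs.

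**Step 5: illustrative counts, with an assumed rate.** Take 2 to 20 SAEs per 100 patient-years, 50 patients, a full 30-day screening and no exclusions.
- Before first dose: 50 × 30/365.25 = 4.11 patient-years; × 0.02 to 0.20 = 0.08 to 0.82 events.
- In the 42 days from first dose: 50 × 42/365.25 = 5.75 patient-years; × 0.02 to 0.20 = 0.11 to 1.15 events.

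The pre-dose figures are ceilings under that assumption, because some patients with a screening SAE would not go on to be dosed.

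**Step 6: would the TEAE window serve as the filter?** No.
- With a last dose on Day 28, the SAP's TEAE window closes before Day 28 + 14 = Day 42. The PTFU Visit is Day 42 ±3, so SAEs from Day 42 up to a visit as late as Day 45 would be dropped.
- A patient who stops drug on Day 8 may remain in the study (protocol 5.4.1). The window would close before Day 8 + 14 = Day 22, and any SAE from Day 22 on would leave the row.

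**The case against.** **The definitions may already exclude these events.** The SAP ties an AE to use of a drug, and protocol 8.1.1 refers to a patient who has been given a product. The endpoint wording in the protocol summary could also be read as applying *treatment-emergent* to both TEAEs and SAEs. This leaves some ambiguity. It sits badly, however, with explicit SAE collection from consent, with the use of TEAE in some rows and not others, and with the Appendix 3 rule for pre-dose onsets.

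**The consequence is small.** This largely stands:
- SAP 12.6 plans no formal safety statistics, so the table is descriptive.
- 12.6.1 does not itself say that this table is by arm; that follows from protocol 9.1 and the as-treated rule.
- SAEs are listed separately, and protocol 8.3 records whether onset was before, during or after application, so a reader could identify a pre-dose event.
- Eligibility is rechecked on Day 1. Inclusion requires good general health, and systemic infection within 3 months or systemic antibiotics within 30 days of Day 1 exclude. Many patients with a screening SAE would never be dosed.

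**Stronger readings that a reader might infer, which the documents do not support:**
- *Every SAE and death row is affected.* The causality definition and the FAS definition protect the treatment-related SAE and death rows.
- *About 42% of tabulated SAEs would be pre-dose.* That figure needs a full 30-day screening and a constant rate among patients who are later dosed.
- *The comparison is biased toward one arm.* Events before randomisation cannot be caused by assignment and are balanced in expectation. They add noise.
- *Collection from consent is wrong.* The gap is in tabulation, not in collection.

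**Conclusion.** The point holds for the *Any SAE* row of SAP 12.6.1 and the matching endpoint wording, and for nothing else in that table. As written, a screening SAE in a patient later dosed enters that arm's SAE incidence, and no text in either document removes it.

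One such patient shifts an arm by 4.0 points at 25 per arm or 4.8 points at 21 per arm. The expected number is small and cannot be fixed from the documents, since they give no SAE rate. This conclusion assumes that the row is programmed literally and shown by treatment group. It is a minor correction, but worth making before unblinding because the row reports a named endpoint and a single event is visible at this sample size.

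**What to change.** 1. In SAP 12.6.1, define the row as *Any SAE with onset on or after the first dose*, counted through the end of SAE collection: the PTFU Visit or 14 days after the last application, whichever is later. Do not use the TEAE window. It would drop post-dose SAEs (step 6), and it is not stable across the documents: protocol 9.4.6 runs TEAEs to the end of the study, while protocol 8.1.1 and SAP 12.6.1 stop short of 14 days after the last dose.
2. Show SAEs with onset before the first dose only in the SAE listing, flagged *pre-treatment*.
3. Align the endpoint wording in protocol 3.4 and 9.4.4 and in SAP 9.1.
4. Leave collection from consent as it is. The treatment-related SAE and death rows need no change.

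The cost is a few lines of wording, one onset filter and one listing flag. Onset relative to application is already recorded, and Appendix 3 already covers partial dates, so no new data are needed.
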